1 PROTOCOL SUMMARY

1.1 Synopsis

Protocol title

A Phase 3 Multicenter, Double-Blind, Randomized, Placebo-Controlled Study to Evaluate the Efficacy, Safety, and Tolerability of Rozanolixizumab in Adult Study Participants with Persistent or Chronic Primary Immune Thrombocytopenia (ITP)

Short title

A Phase 3 study evaluating the efficacy, safety, and tolerability of rozanolixizumab in adult study participants with ITP

Rationale

Immune thrombocytopenia is a clinical disorder in which thrombocytopenia manifests as a bleeding tendency, purpura, or petechiae. Autoantibodies against platelet antigens are considered to be a hallmark of ITP. Production of pathogenic immunoglobulin (Ig) G autoantibodies by plasma cells is accepted as the central underlying pathophysiological mechanism in a number of IgG-mediated autoimmune diseases, which includes ITP. In some patients, antibodies recognize antigens derived from a single glycoprotein; whereas in others, antibodies recognize multiple glycoproteins. The spleen is the key organ in the pathophysiology of ITP, not only because platelet autoantibodies are formed in the white pulp, but also because mononuclear macrophages in the red pulp destroy immunoglobulin-coated platelets.

Treatments aimed at reducing the quantity of circulating IgG autoantibodies are being used for primary and secondary therapy of autoimmune diseases including ITP, particularly where corticosteroid-based immune suppression is not or no longer effective. The therapeutic approach of these treatments is based on lowering levels of pathogenic autoantibodies, which represents rational and effective treatment modalities of autoimmune diseases. The primary goal for treatment of ITP is to achieve a platelet count that prevents major bleeding, rather than correcting the platelet count to normal levels.

Rozanolixizumab is a humanized IgG4P monoclonal antibody that is being developed as an inhibitor of the activity of neonatal Fc receptor (FcRn). The FcRn receptor recycles IgG and albumin and transports it bidirectionally across epithelial barriers. Recent studies have shown that FcRn rescues both IgG and albumin from intracellular lysosomal degradation by recycling it from the sorting endosome to the cell surface (Anderson et al, 2006). Rozanolixizumab has been specifically designed to block IgG binding to FcRn without blocking the binding and recycling of albumin. By blocking the activity of FcRn, rozanolixizumab accelerates the catabolism of IgG antibodies, including IgG autoantibodies. This Phase 3 study, TP0003, will be one of 2 studies that will provide the required data to establish the efficacy and safety of rozanolixizumab over placebo in study participants with persistent or chronic primary ITP who have failed or were intolerant to two or more prior ITP therapy and who require an increase and sustained effect in their platelet counts.

Objectives and endpoints

Objectives	Endpoints
Primary	

 To demonstrate the clinical efficacy of rozanolixizumab in maintenance treatment in study participants with primary ITP 	
The primary efficacy endpoint is:
 
 Durable Clinically Meaningful Platelet Response of $\geq 50 \times 10^9/L$, for at least 8 out of 12 weeks during the last 12 weeks (Week 13 to 25) 
The secondary efficacy endpoints are:
 
 Cumulative number of weeks with Clinically Meaningful Platelet Response of $\geq 50 \times 10^9/L$ over the 24-week treatment period Time to first Clinically Meaningful Platelet Response of $\geq 50 \times 10^9/L$: time from starting treatment to achievement of first response of $\geq 50 \times 10^9/L$ Clinically Meaningful Platelet Response of $\geq 50 \times 10^9/L$ by Day 8 Response defined as platelet count $\geq 30 \times 10^9/L$ and at least a 2-fold increase of the Baseline count confirmed on at least 2 separate occasions at two adjacent nominal visits at least 7 days apart, and absence of bleeding by visit ^{a,b} Time to first rescue therapy Change from Baseline to Week 25, in ITP Patient Assessment Questionnaire (ITP-PAQ) Symptoms Score 
The other efficacy endpoints are:
 
 Duration of first Clinically Meaningful Platelet Response of $\geq 50 \times 10^9/L$: measured from achievement of first Response to loss of first Response (loss of Response defined as platelet count $< 50 \times 10^9/L$) Time to first Response: time from starting treatment to achievement of Response Usage of rescue therapy by visit

	
 • Complete Response defined as platelet count $\geq 100 \times 10^9/L$ confirmed on at least 2 separate occasions at two adjacent nominal visits at least 7 days apart, and absence of bleeding by visit ^{a,b} • Cumulative number of weeks over the planned 24-week treatment period with platelet count of $\geq 100 \times 10^9/L$. • Cumulative number of weeks over the planned 24-week treatment period with platelet counts $\geq 30 \times 10^9/L$ and at least doubling from Baseline. • Mean change from Baseline in platelet count by visit. • Clinically Meaningful Platelet Response of $\geq 50 \times 10^9/L$, for at least 4 out of 6 weeks during the last 6 weeks (Week 19 to 25). • Clinically Meaningful Platelet Response of $\geq 50 \times 10^9/L$, for at least 6 out of 8 weeks during the last 8 weeks (Week 17 to 25).
Secondary	

 • To assess the safety and tolerability of rozanolixizumab 	
The safety endpoints are:
 
 • Occurrence of treatment-emergent adverse events (TEAEs) • Occurrence of TEAEs leading to withdrawal of investigational medicinal product (IMP) (ie, study discontinuation) 
The other safety endpoints are:
 
 • Occurrence of serious TEAEs • Occurrence of treatment related TEAEs • Occurrence of adverse events of special monitoring (AESM) • Vital signs change from Baseline (blood pressure [BP], pulse rate, body temperature) at each scheduled assessment during Treatment and Safety Follow-up (SFU) Periods

	
 • 12-lead electrocardiogram (ECG) change from Baseline at each scheduled ECG visit • Laboratory change from Baseline (hematology including coagulation parameters, clinical chemistry, and urinalysis) at each scheduled assessment during Treatment and SFU Periods • Change from Baseline in concentrations of total protein and albumin • Change from Baseline in serum complement levels (C3 and C4) and plasma complement levels (C3a and C5a) at each scheduled assessment during the study (for study participants experiencing infusion reactions or hypersensitivity reactions)
Exploratory	

 • To evaluate the clinical efficacy as measured by the ITP bleeding score 	
 • ITP-specific Bleeding Assessment Tool (ITP-BAT) bleeding events and severity by visit

 • To assess the effect of rozanolixizumab on health-related quality of life (HRQoL) 	
 • Change from Baseline in European Quality of Life (EuroQol) -5 dimension 5 Levels (EQ-5D-5L) item responses • Change from Baseline in Short form 36-item (SF-36) domain and composite scores • Change from Baseline in the ITP-PAQ domain scores

 • To assess hospitalizations due to ITP 	
 • Number and length of hospitalizations

 • To assess the effect of rozanolixizumab on patient reported outcomes (PROs) 	
 • Change from Baseline in FATIGUE-PRO Physical Fatigue Score • Change from Baseline in Patient Global Impression of Severity (PGI-S) • Patient Global Impression of Change (PGI-C) at all available post-baseline assessments

 • To assess the pharmacokinetics of rozanolixizumab administered by subcutaneous (sc) infusion 	
 • Plasma concentration of rozanolixizumab

 To evaluate the incidence and emergence of antidrug antibodies (ADAs) of rozanolixizumab 	
 ADAs at each scheduled assessment

 To assess the pharmacodynamic (PD) effects of rozanolixizumab 	
The exploratory PD endpoints are:
 
 Total serum IgG (absolute value) and change from Baseline (absolute value and percentage) in serum IgG and in serum IgG subclass concentration at each scheduled assessment Absolute values and change from Baseline (absolute value and percentage) in serum immunoglobulin concentrations (IgA, IgE, IgM) at each scheduled assessment

 To assess the influence of rozanolixizumab treatment on vaccination titers 	
 Percent change from Baseline in vaccination titers against Streptococcus pneumoniae, Neisseria meningitidis, and Haemophilus influenzae in splenectomized study participants Percent change from Baseline in vaccination titers against tetanus in all study participants

 To assess the effect of rozanolixizumab on response to vaccination in study participants who received COVID-19 vaccine 	
 Change in biomarkers of COVID-19 vaccine response over time

^a Absence of bleeding indicated by Grade 0 for all domains of the skin, mucosae, and organs (SMOG), or a Skin Grade of 0 or 1.

^b Nominal visits are on-site visits where ITP bleeding scale assessment is performed.

Overall design

This is a Phase 3, multicenter, double-blind, randomized, placebo-controlled study with rozanolixizumab in study participants with persistent or chronic primary ITP defined as more than 3 months, or more than 12 months of duration respectively, since diagnosis.

The study participants will be male and female adults with persistent or chronic primary ITP, history of prior ITP treatment, a platelet count measurement at Screening (Visit 1) and at Baseline with an average of the two $<30 \times 10^9/L$ (no single count may be $>35 \times 10^9/L$) and a documented history of low platelet count ($<30 \times 10^9/L$) any time prior to Screening.

Participants should previously have received two or more ITP therapies and should have initially responded to such therapy and have a current or history of a blood smear consistent with primary ITP.

Study participants who have previously undergone a splenectomy will be included in the study provided they do not meet the protocol defined exclusion criteria (Section 5.2) in order to optimize protection against overwhelming post-splenectomy infection (OPSI). Splenectomized study participants should be vaccinated against the encapsulated organisms, such as *Streptococcus pneumoniae* (*S. pneumoniae*), *Neisseria meningitidis* (*N. meningitidis*), and *Haemophilus influenzae* (*H. influenzae*) (as per local/or national guidance, as applicable) as evidenced from immunization records or during the Prolonged Screening Period. Study participants, who are due to receive a booster, can be screened after they received the required booster.

Splenectomized study participants will be required to attend a Prolonged Screening Period prior to the Screening Visit to receive, if applicable, the required vaccinations (see Table 1-3).

The study will assess whether multiple sc infusions of rozanolixizumab will result in a durable Clinically Meaningful Platelet Count of $\geq 50 \times 10^9/L$, for at least 8 out of 12 weeks during the last 12 weeks of the Treatment Period (Weeks 13 to 25). Starting at Week 2, platelet counts will be measured every week at a local laboratory. Home visits including home dosing and assessments as per Section 1.3 can be conducted once all pre-requisites for a home dosing visit are fulfilled.

Once eligibility is confirmed on Day 1 (Baseline Visit), study participants will enter the Treatment Period (24 weeks) and will be randomized 2:1 to receive a fixed-unit dose of rozanolixizumab equivalent to [REDACTED] or placebo once a week (QW) with randomization stratified by the degree of thrombocytopenia (platelet count $<$ or $\geq 15 \times 10^9/L$) and history of splenectomy (yes or no). The last assessment of the Treatment Period will take place at Week 25.

During the first 12 weeks in the study (Week 1 until Week 12) IMP dose adaptations, depending on the observed levels of platelets as detailed in Table 1-1, will be allowed. The Dose Adaptation Period aims at achieving an IMP dose regimen that sustains a platelet count $\geq 50 \times 10^9/L$ to $\leq 150 \times 10^9/L$ until the beginning of Week 13. Following the initial dose equivalent to [REDACTED], subsequent QW doses can be adapted to dose equivalents to [REDACTED] QW or [REDACTED] total dose (corresponding to an average [REDACTED] dose in a participant weighing 70kg) QW based on the platelet count. Following this Dose Adaptation Period, study participants will enter the Maintenance Period starting at Week 13 until Week 25. The dose regimen that achieves platelet stabilization in the adaptation period will be continued throughout the Maintenance Period. During the Maintenance Period the dose regimen should remain stable and further dose adaptations should be avoided if possible. However, adjustments for safety and efficacy reasons will still be allowed as outlined in Table 1-1 and Figure 1-1, which presents the dose titration for IMP based on the platelet count.

Table 1-1: Dose adjustments of IMP following initial dose

[figure not shown]
Platelet count result ^a	Dose adjustment (based on weekly platelet counts)
<10×10 ⁹ /L	Rescue therapy is highly recommended as per Section 6.4.3.
≥10×10 ⁹ /L to <30×10 ⁹ /L (on at least two consecutive visits)	Rescue therapy is recommended as per Section 6.4.3.
≥30×10 ⁹ /L to <50×10 ⁹ /L (on at least two consecutive visits)	Increase by one dose level, unless study participant is on maintenance dose of ██████
≥50×10 ⁹ /L to ≤150×10 ⁹ /L ^b	Continue with current dose level
>150×10 ⁹ /L to <400×10 ⁹ /L (on at least two consecutive visits)	Decrease by one dose level, unless study participant is on maintenance dose of ██████
≥400×10 ⁹ /L	Stop IMP treatment. Once the platelet count is ≤150×10 ⁹ /L, reinitiate treatment decreased by one dose level

^a All analyses of platelet counts will be based on local laboratory results

^b Due to the interindividual variable platelet response, in some study participants platelet count may abruptly fall below 50×10⁹/L after dose reduction or treatment discontinuation. In these cases, if clinically appropriate, higher cut-off levels of platelet count for dose reduction (>150×10⁹/L) may be considered according to medical judgment, but should not exceed 250×10⁹/L.

For the dose adjustments where a decrease is required, study participants receiving ██████ should continue at this dose level, as dose reductions below ██████ are not applicable. If a study participant is in the lowest body weight tier (below 50kg) and is on the lowest dose level with a platelet count between >150×10⁹/L and <400×10⁹/L, the investigator might decide to temporarily stop treatment according to medical judgment based on the observation of platelet variability. If the platelet count increases to above 400×10⁹/L, then IMP must be stopped.

Figure 1-1: TP0003 dose adjustments of IMP

eqv=equivalent; QW=once a week

Dose adaptations may start as early as Week 2

* eqv: fixed-unit dose with body weight tiers equivalent to the mg/kg dose in terms of IgG reductions and safety profile

If treatment as per Table 1-1 and Figure 1-1 does not lead to an increase in platelet count $\geq 30 \times 10^9/L$, the study participant can be treated with rescue therapy, if deemed needed by the investigator. If platelet count is $\geq 10 \times 10^9/L$ to $< 30 \times 10^9/L$ or active bleeding, rescue therapy is recommended (eg, commercially available medication, such as intravenous immunoglobulin [IVIg], high dose corticosteroids and pulse steroids, platelet transfusions, or any other medication listed in Section 6.4.3). If platelet count is $< 10 \times 10^9/L$, rescue therapy is highly recommended as per Section 6.4.3. If a study participant has been down-titrated to a fixed-unit dose equivalent to [redacted] total dose (corresponding to an [redacted] dose in

a participant weighing 70kg), and platelet count decreases to less than $50 \times 10^9/L$, then up-titration to a fixed-unit dose equivalent to █████ QW or █████ QW, respectively, would be allowed.

Study participants should be monitored for signs of arterial or venous thrombotic and thromboembolic events. If such events occur, the investigator should undertake the appropriate management per medical judgment and local guidance, and contact the Medical Monitor. Thrombotic or embolic events are considered AESM, as described in Section 8.3.8, and the reporting rules can be found in Appendix 3, Section 10.3.

All study participants completing the Treatment Period (regardless of whether they received rescue therapy or not) and fulfilling the open-label extension (OLE) study (TP0004) eligibility criteria will be allowed to enroll into the 1-year OLE treatment study TP0004. The enrollment into the TP0004 study should be conducted on the same day as Visit 27 (Week 25) of the feeder study. In case the enrollment into TP0004 is not conducted at Week 25 (Visit 27), a visit window of +3 days will be granted; therefore, rollover needs to be completed 3 days after Week 25 at the latest.

Participants that will not be enrolling into the OLE study will be followed for up to 8 weeks after the last administration of IMP. The End of Study (EOS) Visit will be performed after the SFU Period.

An external Independent Data Monitoring Committee (IDMC) will be established to review the safety data at predefined intervals and ad hoc as needed should emerging safety concerns arise during the study. The first IDMC meeting for the review of safety data is planned to occur after approximately 15 participants have received 3 doses of IMP in TP0003. The study will be put on hold if any of the following occurs

- The IDMC judges it necessary for medical or safety reasons and
- The sponsor or its designee judges it necessary for medical, safety, regulatory, or any other reasons consistent with applicable laws, regulations and Good Clinical Practice.
- Three study participants experience any serious adverse event (SAE) of the same type within the first 15 study participants who have received 3 doses of IMP across TP0003 and TP0006, unless the SAE is clearly unrelated to the study drug.
 - **For US and Canada only:** Three study participants experience any SAE within the first 15 study participants who have received at least one dose of IMP across TP0003 and TP0006, unless the SAE is clearly unrelated to the study drug.

It is intended to have one IDMC for both of the pivotal studies (TP0003 and TP0006), where the safety data will be initially presented unpooled, ie, data from each study will be reviewed separately. Key safety data may be pooled at the discretion of the IDMC for protection of all study participants if warranted.

Based on feedback from the IDMC, weekly dosing was implemented in protocol amendment 3. Study participants being treated with the bi-weekly dosing regimen will switch to the weekly dosing regimen once protocol amendment 3 is approved at the respective study site. Additionally, the sponsor's Safety Signal Detection Team will perform aggregated safety data reviews at predefined intervals across all rozanolixizumab programs.

For **Japan** specific regulations, see Appendix 8, Section 10.8.

Number of participants

Study participants will be randomly assigned to IMP in a 2:1 ratio to either rozanolixizumab or placebo, respectively. The total sample size will be approximately 90 study participants, at least 60 of which will be randomized to weekly IMP administration (for determination of sample size, see Section 9.8).

Treatment groups and duration

The total maximum study duration per study participant is up to 35 weeks, consisting of a Screening Period (up to 4 weeks), a Dose Adaptation Period (12 weeks), a Maintenance Period (12 weeks) and a SFU Period (8 weeks after final dose administered). The eligibility of study participants to participate in the study will be determined during the Screening Period (Day -28 to Day -1). Splenectomized participants will be required to attend a Prolonged Screening Period prior to the Screening Visit to assess and receive, if applicable, the required vaccinations, which will extend the total study duration by up to 20 weeks.

Fixed-unit doses across body weight tiers and treatment arms will be employed in this study according to the following scheme, as presented in Table 1-2.

Table 1-2: TP0003 dose levels and weight tiers of IMP

Dose* eqv \ Bodyweight	Dose level 1	Dose level 2	Dose level 3
>35 to <50kg			No weight adjustment
≥50 to <70kg			
≥70 to <100kg			
≥100kg			

eqv=equivalent; IMP=investigational medicinal product

[figure not shown]
If a study participant is in the lowest body weight tier (below 50kg) and is on the lowest dose level with a platelet count between $>150 \times 10^9/L$ and $<400 \times 10^9/L$, the investigator might decide to temporarily stop treatment according to medical judgment based on the observation of platelet variability. If the platelet count increases above $400 \times 10^9/L$ then treatment must be stopped anyway.

The placebo arm will use 0.9% sodium chloride aqueous solution (physiological saline, preservative free) for sc administration, matching the volumes of the rozanolixizumab arm.

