generally [REDACTED] and well tolerated, with an acceptable safety profile and no new safety concerns were identified.

In addition, in order to avoid platelet count increases to $\geq 150 \times 10^9/L$, down-titration of the IMP dose level as described in Table 1-1 will be allowed. Weekly platelet assessments will be performed during the study, to support the dosing strategy with the aim to increase platelet counts $\geq 50 \times 10^9/L$ and to minimize platelet counts $\geq 150 \times 10^9/L$ in the study participants. Up titration to fixed-unit doses of [REDACTED] rozanolixizumab [REDACTED] QW will also be allowed to maintain stable platelet counts of $\geq 50 \times 10^9/L$ over the Treatment Period if a previous down titration has occurred and subsequently platelet counts dropped again to below $50 \times 10^9/L$.

In summary, the new proposed dose regimen for Phase 3 is a [REDACTED] QW dose as starting and maintenance dose, allowing to down-titrate to [REDACTED] total dose based on the efficacy and safety profile. This regimen is supported by the observed data in the program thus far.

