6.4.3 Rescue therapy

Rescue treatment will be given as per standard of care and at the discretion of the investigator as described below. If such rescue therapy is given, the participant is allowed to continue IMP treatment (as per guidance below), and should continue to complete all remaining scheduled visits in the Treatment Period, as per the Schedule of Activities (Section 1.3). The following rescue therapies may be used:

- Any increase in concomitant ITP therapies above Baseline dose
- Any additional ITP medication/therapies including but not limited to:
 - Platelet transfusion (only in cases of severe bleeding)
 - Commercially available IVIg
 - Any systemically administered corticosteroids (above the background doses, ie, pulse, oral and iv steroids). Any systemic corticosteroids used for the management of infusion reactions or other medical conditions are also considered rescue therapy.
 - Immunosuppressants (except for those listed in Section 6.4.2).

Although the use of rescue therapy is allowable at any time during the study, the use of rescue therapy should be delayed, if possible, for at least 2 days following the administration of study treatment.

If IVIg, high dose corticosteroids, or platelet transfusion are given as rescue therapy, IMP treatment can commence at the same dose as previously when platelet counts are $<50 \times 10^9/L$. Dose can be up-titrated at a later timepoint, if needed, depending on platelet level.

A high dose of corticosteroids is defined as any iv administration of corticosteroids given for any reason or doubling of an oral dose resulting in a dose more than 20mg/day prednisone equivalent dose.

In case of an increase of Baseline oral corticosteroids, not resulting in doubling of the oral dose more than 20mg/day prednisone equivalent dose, an increase in the concomitant ITP therapies above Baseline, or in case of administration of immunosuppressants as rescue therapy, IMP administration can continue as per Schedule of Activities (Section 1.3) at a dose adjusted depending on the platelet level.

The date and time of rescue therapy administration as well as the name and dosage regimen of the rescue therapy must be recorded in the eCRF.

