8.1 Statistical analysis of the primary efficacy endpoint

8.1.1 Primary analysis of the primary efficacy endpoint

The primary efficacy endpoint will be analyzed according to the following estimands' attributes:

- (1) Treatment conditions: Placebo and rozanolixizumab (please refer to section 6 Study treatments in the protocol for details)
- (2) Population: Adult Study Participants with Persistent or Chronic Primary Immune Thrombocytopenia (ITP) who fulfill the inclusion / exclusion criteria according to the protocol.
- (3) Endpoint: Durable Clinically Meaningful Platelet Response of $\geq 50 \times 10^9/L$, for at least 8 out of 12 weeks during the last 12 weeks (Week 13 to Week 25)
This endpoint includes the platelet count recorded at Week 14 to Week 25 corresponding to the response achieved following dosing at Week 13 to Week 24)
- (4) Intercurrent Events: see below.

Table 8-1: Intercurrent Events (ICE), Intercurrent Events Strategies (ICES) and Missing data Strategies for the analysis of the primary endpoint

Intercurrent Events (ICE)	ICE Strategy	Missing data strategy
a) Use of Rescue therapy from Baseline prior Week 25	A composite strategy Participants impacted by any ICE (a, b, c and d) will be considered as non-responders after the time of event.	Not applicable Section 4.2.2
b) Participants who experience any TEAEs leading to permanent treatment discontinuation		
c) Participants who discontinue prior to receiving IMP		
d) Participants who do not have any post-treatment assessment		
e) COVID-19*	A composite strategy Participants impacted by ICE (e) will be considered as non-responders at the time of event.	

* COVID-19 Impact category: Temporary discontinuation of study drug, Permanent discontinuation of study drug, Termination of study participation and Relationship to COVID-19: confirmed, suspected, general or other as recorded in the COVID-19 impact eCRF form.

(5) Population-level summary: Owing to early termination of the study, the population-level summary will be provided using descriptive statistics.

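### Table 1-1 and the surrounding text set different triggers, for raising the dose and for rescue, once a down-titrated participant's platelet count falls below 50×10⁹/L

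*Protocol*

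**What the plan says.** All counts are in 10⁹/L.

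- **Protocol 1.1, Table 1-1.** One row raises the dose, at 30 to <50 seen at two visits running: "Increase by one dose level, unless study participant is on maintenance dose of" a redacted level. At 10 to <30, again at two visits running, the entry is "Rescue therapy is recommended as per Section 6.4.3". Below 10, on any count, it is "Rescue therapy is highly recommended as per Section 6.4.3". Neither row below 30 mentions the IMP dose.
- **Protocol 1.1, text below Figure 1-1.** The up-titration rule opens "If a study participant has been down-titrated to a fixed-unit dose equivalent to" a redacted dose and continues "and platelet count decreases to less than $50 \times 10^9/L$, then up-titration to a fixed-unit dose equivalent to" redacted levels, which would be allowed. It has no lower bound and no two-visit condition. The same paragraph recommends rescue at 10 to <30, or with active bleeding, also without a two-visit condition, and recommends it strongly below 10.
- **Protocol 4.3.** Up-titration is allowed "if a previous down titration has occurred and subsequently platelet counts dropped again to below $50 \times 10^9/L", again with no lower bound and no number of visits.
- **Protocol 6.4.3.** After platelet transfusion, IVIg or high-dose steroid, "IMP treatment can commence at the same dose as previously when platelet counts are $<50 \times 10^9/L", and the dose may be raised later. After other rescue, IMP continues at a dose that follows the platelet level.
- **SAP 8.1.1, Table 8-1.** The first intercurrent event for the primary endpoint is "Use of Rescue therapy from Baseline prior Week 25", handled as nonresponse from that time on. Protocol Table 9-1 also counts rescue as nonresponse. Neither table lists a dose change as an intercurrent event.

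**The concern.** The Dose Adaptation Period is meant to find a dose that holds the count between 50 and 150 by the start of Week 13. Section 4.3 describes the starting dose as the maintenance dose, from which participants may step down. The up-titration rule therefore concerns people who overshot, were reduced and then fell again. Footnote b of Table 1-1 expects such falls after a reduction. Even so, the table and the text answer three questions differently for this group: at which counts the dose may go up, whether one count is enough, and when rescue is recommended.

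The answers bear on the primary endpoint because rescue ends the chance of response and a dose step does not. They bear on safety because the table gives no IMP action at the lowest counts.

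**Working it through.** No sample size or power formula applies, so the check sets the two rules side by side. It takes a participant already down-titrated and reads the table literally, with its two-visit conditions, against the text under Figure 1-1. The pairs are illustrations and not frequencies.

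| Previous, current count | Table 1-1 | Text under Figure 1-1 |
|---|---|---|
| 40, 40 | raise one level | up-titration allowed |
| 80, 40 | no row met | up-titration allowed |
| 20, 40 | no row met | up-titration allowed |
| 80, 20 | no row met | rescue recommended; up-titration allowed |
| 40, 20 | no row met | rescue recommended; up-titration allowed |
| 5, 20 | no row met | rescue recommended; up-titration allowed |
| 20, 20 | rescue recommended; no dose entry | rescue recommended; up-titration allowed |
| 80, 5 | rescue highly recommended; no dose entry | rescue highly recommended; up-titration allowed |

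1. **Dose.** The two sources agree in one of the eight pairs (40, 40). In the other seven the text allows a dose step and the table has none.
2. **Rescue.** The two sources differ in three pairs (80, 20; 40, 20; 5, 20). The text recommends rescue on one count where the table waits for a second.
3. **Alternating counts.** In 25, 45, 25, 45 no two successive counts share a band, so no table row is ever met although every count is below target. Under the text, each 25 meets the rescue recommendation and every count allows up-titration.
4. **After rescue.** For rescue other than transfusion, IVIg or high-dose steroid, Section 6.4.3 ties the dose to the platelet level. If that leads back to Table 1-1, there is no dose entry below 30 to apply.
5. **Endpoint.** The primary variable needs at least 8 of the 12 weekly counts from Week 14 to Week 25 to be ≥50 (Protocol 9.3.1). A participant rescued at Week 10, say, is a nonresponder whatever the later counts. One whose dose was raised at Week 10 without rescue can still respond.
6. **Direction.** At a first count of 20, the table triggers nothing and the text recommends rescue, so a site following the text is more likely to create a nonresponder. At a first count of 40, only the text allows an earlier dose step, which could help response. The net effect on response rates has no clear sign.

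**The case against.** The strongest reply is that nothing here is truly incompatible. The text is permissive, the table rows below 30 are silent on dose and do not forbid a step, rescue is left to the investigator, and Section 6.5 permits dose changes to keep the count between 50 and 150. A site could give rescue and raise the dose without breaching either passage. For the dose below 30 this stands: it is a gap in the table, not two opposing orders. It does not remove the differing two-visit conditions, which are stated triggers for the same counts.

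A reader might also infer that the table forces rescue at the reduced dose. The documents do not say so. The rows below 30 give no dose. The same-dose restart in Section 6.4.3 covers only three kinds of rescue and is followed by permission to raise the dose later.

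A reader might further infer a loss of power, with would-be responders rescued instead of re-titrated. That is not supported either. The text that allows up-titration also recommends rescue below 30, so harmonising the dose wording would not by itself prevent the nonresponse. The documents give no share of participants who overshoot, are reduced, fall below 30 and are rescued.

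Finally, Figure 1-1 is not shown and dose levels are redacted. The figure may state an action below 30, though Table 1-1 and the text would still differ.

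**Conclusion.** The inconsistency is real. For a down-titrated participant below 50, Table 1-1 and the text differ on the range of counts that allows a dose step, on whether one count or two is needed, and on when rescue is recommended at 10 to <30. Mixed-band sequences meet no table row. Sites could handle identical counts differently, with consequences for primary response and for care at low counts.

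Its size cannot be put in numbers from the documents, and its direction is not fixed. It does not touch the reported results. The SAP states that nobody was randomized under Amendment 3 or moved to weekly dosing, that all 33 participants were on earlier versions, and that efficacy is only described. It is a correction worth making to the protocol as a plan, not a defect that undermines the trial. The conclusion rests on a literal reading of the table and on Figure 1-1 not resolving the point.

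**What to change.** Reconcile Table 1-1, Figure 1-1, the text below the figure, Section 4.3 and Section 6.4.3 so that each states the same rule. That rule should say:

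- what happens to the IMP dose of a down-titrated participant at each count below 50, including below 30;
- at what counts rescue is recommended;
- for each action, whether one count or two is needed;
- whether successive counts in different bands below 50 count as consecutive;
- how the restart and dose-adjustment sentences in Section 6.4.3 apply when the count is below 30.

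Which rule to adopt is for the sponsor's clinicians. The cost is amendment wording in one table, one figure and three passages of text, with no new visits, assessments or participants.
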